11. ANALYSIS OF SAFETY ENDPOINTS

All analyses presented in this section will be done using the Safety set.

11.1 Exposure

Duration of exposure to study drug (months) is based on the number of days a patient received drug and is defined as

(Last day of study drug – the first day of study drug + 1)*12/365.25.

Duration of exposure (months) will be summarized using descriptive statistics by treatment arm. The analysis will be repeated for all subgroups defined in Section 7.4.

The cumulative exposure (over all patients within treatment arm) in person-months will be provided.

The number of partial or complete infusions that a patient received will be summarized by treatment arm and by location of administration (home/site). Summary of infusion duration (hours) by visit will be presented by treatment arm.

Listing of infusion should include whether the complete dose was administered or not.

11.2 Adverse Events

Adverse events (AE) will be coded by the Medical Dictionary for Drug Regulatory Activities (MedDRA) version 19.00 or higher.

Pre-treatment AEs include all AEs occurred prior to the first study drug infusion. Pre-treatment AE will only be presented in listings.

A Treatment-emergent AE (TEAE) is defined as any AE that started post–first infusion. In case that date of onset is completely unknown, the AE will be classified as TEAE. In case the date is partially known, it will be classified as TEAE unless there is evidence, from the partial info (e.g., month of AE onset is earlier than the month of first infusion), that the AE was pre-treatment.

The number and percentage of patients with at least one TEAE and the number of TEAE will be reported by treatment arm and overall for the following parameters: Any TEAE; Related (showing jointly possibly, probably or definitely related events) TEAE; Mild or moderate TEAE; Related mild or moderate TEAE; Severe TEAE; Related severe TEAE; Serious AEs; Non- Serious AEs; Related serious AE; TEAE leading to withdrawal; Related TEAE leading to withdrawal; TEAE leading to death; and Treatment related TEAE leading to death. For selected summary tables, the

number of events will be shown together with the rate per 100 person-years defined as number of events X 100 / total exposure (in years).

In the analysis of severity, patients with event classified as "Very Severe" per CTCAE severity in eCRF will be presented in the category "Severe" for analysis.

This analysis will be repeated for the following sub-groups: ADA status, gender, FD classification and region.

The overall analysis will be repeated for injection site reaction TEAEs. Injection site reactions will be identified by their SOC and PT, as defined in Table 3 and their start time that should occur within 24 hours from the infusion, following the algorithm described in Section 11.2.3.

TEAE summary tables by the MedDRA SOC and PT will present the number and percentage of patients with at least one TEAE and the number of TEAEs. These tables will be presented by treatment arm; by treatment arm and severity; and by treatment arm and relationship to study drug.

A similar table by SOC and PT will be generated for serious TEAEs by treatment group and overall and by relationship to study drug.

In summary tables by SOC and PT, SOC will be sorted alphabetically. Within SOC, PT will be sorted in a decreasing order of PRX-102 frequency.

In the summaries of severity and relationship to study drug, the most extreme value (highest severity and closest relationship to study drug) will be used for those patients who experience the same TEAE (per PT) on more than one occasion.

Missing values associated with TEAEs will be treated as missing except for causality, severity, and outcome of a TEAE, at which occurrence a "worst case" approach will be taken in the analysis. Thus:

- If causality is missing, the TEAE will be regarded as related to pegunigalsidase alfa
- If the severity is missing, the severity of the TEAE will be regarded as severe
- If the outcome is missing and the stop date is not provided, the outcome is regarded as "ongoing"

If the seriousness is missing, all efforts should be made prior to database lock to make sure that this information is available, if still missing, the worst-case scenario will be assumed.

All TEAEs will be listed (info about seriousness, severity, relationship, action taken, outcome and the TEAE day in study relative to 1st infusion).

Serious TEAE, related TEAE will be listed as well as TEAEs leading to withdrawal or death.

A listing of patient who were infected with COVID-19 will be generated. The TEAE will be identified by the following SOC, PT and LLT: SOC = Infections and infestations; PT = Corona virus infection; LLT = Corona virus infection. For the final analysis, AEs will be reviewed if need to add also reported terms for the identification.

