8.3.2 Adverse Events

8.3.2.1 Adverse Events (AE) and Serious Adverse Events (SAE)

An adverse event (AE) is any untoward medical occurrence in a subject participating in a clinical trial. An adverse event can be any unfavorable and unintended sign, symptom or disease temporally associated with the use of the study medication, whether or not considered related to the study medication. AEs will be collected from the start of treatment until 90 days following the final visit dose. Any events occurring prior to treatment will be recorded on the medical history page with the event name and onset date and end date if not continuing. Pre-existing, known clinically significant conditions observed at screening should be recorded as medical history.

This definition also includes accidental injuries, reasons for any change in medication (drug and/or dose) other than planned titration, reasons for admission to a hospital, or reasons for surgical procedures (unless for minor elective surgery for a pre-existing condition). It also includes adverse events commonly observed and adverse events anticipated based on the pharmacological effect of the study medication. Any laboratory abnormality assessed as clinically significant by the Investigator must be recorded as an adverse event.

A treatment emergent adverse event is any adverse event occurring after start of study medication and within the time of residual drug effect (90 days after the last administration of the study medication), or a pre-treatment adverse event or pre-existing medical condition that worsens in intensity after start of study medication and within the time of residual drug effect.

Adverse events should be recorded as diagnoses, if available. If not, separate sign(s) and symptom(s) are recorded. One diagnosis/symptom should be entered per record. Treatment-related hypersensitivity/infusion reactions are defined in Appendix 3 and can be defined as a single AE at the Investigator's discretion.

Note that death is not an event, but the cause of death is. An exception is the event of sudden death of unknown cause. Note that hospitalization is not an event; however, the reason for hospitalization is. Procedures are not events; the reasons for conducting the procedures are. In general, only the reason for conducting the procedure will be captured as an adverse event. However, if deemed necessary by the Investigator, a procedure can be captured along with the reason for conducting the procedure.

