10.4.1 Adverse Events

Adverse events will be coded to system organ class and preferred term using MedDRA version 9.1 or higher. All adverse events occurring after the initiation of the study treatment (treatment emergent adverse events) will be reported, including events present at baseline that worsened during the study.

Adverse events will be summarized by treatment group to provide visual comparison among the treatment groups with respect to incidence of adverse events (the number of subjects reporting at least one episode of a specific adverse event), incidence of adverse events by severity within body system, incidence of adverse events by attribution within body system, and incidence of adverse events causing withdrawal and incidence of serious adverse events. Regarding severity and attribution summaries, the most extreme outcome (highest severity and closest to study drug related) will be used for those subjects who experience the same adverse event on more than one occasion.

Hypersensitivity reactions will be analyzed as adverse events of special interest using descriptive statistics.

Written narratives will be provided for all serious, unexpected or other significant adverse events that are judged to be of special interest because of their clinical importance.

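### SAP 11.2 omits the protocol's worsening clause, so worsened pre-treatment events may be missing from the TEAE and severity tables unless entered as new AEs

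*SAP*

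**What the plan says.** The SAP's rule rests on onset alone. Section 11.2 reads: "A Treatment-emergent AE (TEAE) is defined as any AE that started" after the first infusion. For anything that began earlier it adds: "Pre-treatment AE will only be presented in listings". SAP 14.3 reserves Listing 16.2.3.2.1 for these records. An AE with a completely unknown onset date counts as treatment-emergent. No upper time limit is given.

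The protocol's definition has two parts. Section 8.3.2.1 counts AEs that occur after the start of study medication and within 90 days of the last dose. Within the same window it also counts "a pre-treatment adverse event or pre-existing medical condition that worsens in intensity after start of study medication". Section 10.4.1, the protocol's statistical text on AEs, says that all AEs after the start of treatment "will be reported, including events present at baseline that worsened during the study". Section 10.4.1 states no 90-day limit.

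SAP Section 1 makes the SAP the governing text for planned analyses where the two documents are inconsistent. Section 13.1 lists eight changes from the protocol and Section 13.2 lists nineteen from the interim SAP. None of them concerns the definition of a TEAE.

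**The concern.** The two documents classify the same event differently, and the narrower rule is the one that will be programmed. The protocol cannot fill the gap, because the SAP takes precedence.

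The clause matters in this population. Every patient must be symptomatic at entry (protocol 6.2.1), so worsening of an existing Fabry symptom is a plausible form of harm. The SAP also expects records that start before treatment: it gives them a listing, and Section 13.2 (item 19) notes that randomization often preceded the first infusion by about two weeks. If such an event deteriorates on treatment and stays on its original record, its onset date keeps it out of the TEAE tables and hence out of the tables by severity. A reader of the study report would not learn from Section 13 that the definition had been narrowed.

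**Working it through.** No sample size, rate or test enters this point, so there is no figure to reproduce. The check is to classify each type of event under both definitions.

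| Type of event | Protocol 8.3.2.1 | SAP 11.2 | Effect of the SAP rule |
|---|---|---|---|
| (a) AE record with onset before infusion 1; worsens on treatment; same record kept | TEAE | not a TEAE | event missed |
| (b) Pre-existing condition; worsens; entered as a new AE dated at worsening | TEAE | TEAE | none |
| (c) Pre-existing condition; worsens; no new AE entered | TEAE | not a TEAE | event missed |
| (d) New AE on treatment or within 90 days of the last dose | TEAE | TEAE | none |
| (e) New AE more than 90 days after the last dose | not a TEAE | TEAE | event added |

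Three things follow.

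1. Dropping the worsening clause can only lower the counts, through (a) and (c). Dropping the 90-day limit can only raise them, through (e). These are separate effects with opposite signs.

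2. Whether (a) and (c) occur depends on how worsening is recorded. Protocol 8.3.2.1 collects AEs from the start of treatment and sends earlier events to the medical history page, with name, onset date and end date. Protocol 8.3.2.2 describes each AE by start date, stop date and intensity, among other items, and follows it until it resolves or is stable. Neither document says that a worsening must open a new record with its own start date. The SAP 11.2 rule that keeps the most extreme severity does not help, because it applies only among events already classed as TEAEs.

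3. For (c), restoring the clause would not be enough. Protocol 8.3.2.1 lists no intensity for a medical-history entry, so worsening cannot be derived from the fields described. It has to exist as an AE record dated at the worsening.

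The reach of (e) is limited. Protocol 8.3.2.1 ends AE collection 90 days after the final visit dose. The exception is a patient who stops early and is still followed: protocol 6.2.4 asks for follow-up over the full study where possible. SAP 16.2 reports 6 discontinuations among 78 patients (6/78 = 7.7%).

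**The case against.** The strongest reply is that nothing is lost in practice. Under protocol 8.3.2.1, existing Fabry pain is medical history and not an AE with an early onset date. If it worsens, the natural route into the data is an AE dated after the first infusion, which the SAP counts. The AE definition also takes in reasons for a change of medication, reasons for hospital admission and clinically significant laboratory abnormalities, and sites ask about health problems since study medication began. Fabry deterioration is analysed as well through the BPI, MSSI, EQ-5D-5L, pain medication and Fabry clinical events. Section 13.1 claims to list only the main changes.

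Much of this stands. Many worsenings will have been entered as new AEs, and the gap may be small. What remains is that no sentence covers every worsening or fixes its onset date, that the SAP itself provides for AE records with a pre-treatment onset, and that those records are excluded by rule whatever happens later. The other endpoints do not replace AE tables by severity.

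A reader might infer three stronger things, which the documents do not support:

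- That the missing 90-day limit also hides events. It widens the definition, and protocol 10.4.1 has no such limit either.
- That infusion-related reactions are lost. SAP 11.2.2 uses the drug administration form, which asks about AEs during or after each infusion and is linked to the AE record, so a loss there is not established.
- That events on open-label PRX-102 would be counted against the control arm. The extension is a separate study, PB-102-F60 (SAP Section 3), and this SAP covers data collected under PB-102-F20.

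**Conclusion.** The contradiction is one of stated rules and does not arise from missing detail. The protocol counts worsening of pre-treatment events in two places, the governing SAP excludes it, and Section 13 is silent. Worsened pre-treatment events may therefore be missing from the TEAE and severity tables.

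This is conditional. It applies where the worsening stayed on a record with a pre-infusion onset, or on the medical history page, and was not entered as a new AE. It would be wrong to read the text as showing that deteriorations are certainly undercounted. The size cannot be derived from the documents. The same rule applies to both arms, and nothing in the documents shows that it favours either. The absent 90-day limit is a separate inconsistency with protocol 8.3.2.1 that can only add events.

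**What to change.** In SAP 11.2, define a TEAE as any AE with onset after the first infusion, or any pre-treatment AE or pre-existing condition that worsens in intensity after the first infusion. State that such a worsening is handled as an AE dated at the time of worsening, with the intensity then reached. Medical-history conditions need this rule because no intensity is described for them.

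Separately, for consistency with protocol 8.3.2.1, state the upper limit of 90 days after the last PB-102-F20 dose. Record the definition in Section 13.

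The cost is a few lines of SAP text and a change to the TEAE flag. SAP 16.2 gives October 2021 as the last patient's last visit, so worsenings not yet entered as AEs would have to be found by data queries. The blinded team can review the pre-treatment AE listing and ongoing medical history for this before database lock. SAP Section 1 says that the SAP will be finalized before that lock, so the change can still be prespecified, and it returns to a definition that the protocol already holds.

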PRX-102 has enhanced pharmacokinetic properties including a half-life ($T_{1/2}$) of approximately 70 hours, and AUC of approximately 400,000 ng/mL*hour for the 1.0 mg/kg dose after one day of treatment (Day 1), which are believed to be the result of the covalent cross-linking to make PRX-102 enzyme a more stable homo-dimer.

The most commonly experienced AEs were fatigue in 6 patients, and nausea and vomiting each in 5 patients. The most commonly experienced AEs that were considered possibly related to the treatment were nausea in 3 patients, chest discomfort and fatigue each in 2 patients.

Two patients each experienced an SAE. One patient experienced a Grade 3 hypersensitivity related serious adverse event of bronchospasm. The second patient experienced renal hematoma following kidney biopsy and was not considered related to the treatment.

Currently, the safety results of the one completed and two ongoing studies showed that PRX-102 is well tolerated with a favorable safety profile, the majority of adverse events being mild and moderate in severity and a low rate of treatment induced antibody formation.

In view of the data it is concluded that dosing of PRX-102 at 1.0 mg/kg every 2 weeks offers the optimal treatment regimen for attenuating disease progression.

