6.2.4 Removal of Subjects from Therapy or Assessment

Reasons for permanent discontinuation include the following:

- The subject experiences two or more Grade 3 toxicities or one or more Grade 4 toxicity considered by the investigator associated with PRX-102 or agalsidase beta treatment (CTCAE v. 4.03, 2010)
- The subject experiences progressive hypersensitivity or severe hypersensitivity that is not allayed with pre-treatment
- The subject requests to discontinue treatment
- The Investigator feels that it is not in the best interest of the subject to continue treatment and/or if the investigator believes that the subject can no longer be compliant with the requirements of the study

For any discontinuation, the Investigator will obtain all the required details and document the date and the main reason for the premature termination. If the reason for discontinuation is an adverse event, the specific event or the main laboratory abnormality will be recorded in the eCRF. The Investigator will make thorough efforts to document the outcome. The Investigator will attempt to continue to follow the subject for the full duration of the study or at least for 90

days following discontinuation. If circumstances prevent the subject from completing all visits, every attempt will be made to complete all procedures listed in Section 9 for Visit 53.

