An overdose or medication error is not an adverse event unless it is temporally associated with an unfavorable or unintended sign or symptom.

Each AE is to be classified by the investigator as serious or non-serious. A serious adverse event (SAE) is any untoward medical occurrence or effect that occurs at any dose:

- Results in death
- Is life-threatening (i.e., an immediate risk of death)
- Requires in-patient hospitalization or prolongation of existing hospitalization
- Results in persistent or significant disability/incapacity
- Is associated with a congenital anomaly/birth defect
- Is an important medical event

An adverse event caused by an overdose or medication error is considered serious if a criterion listed in the definition above is fulfilled.

Important adverse events that may not result in death, may not be life-threatening, or do not require hospitalization may be considered serious when, based upon appropriate medical judgment, they may jeopardize the subject's safety or may require medical or surgical intervention to prevent one of the outcomes listed above.

Serious adverse events also include any other event that the investigator or sponsor judges to be serious or which is defined as serious by the regulatory agency.

The investigator is to report all directly observed adverse events and all adverse events spontaneously reported by the trial subject using concise medical terminology. In addition, each trial subject will be questioned about adverse events. The question asked will be "Since you began taking the study medication, have you had any health problems?"

8.3.2.2 Procedures for Assessing, Recording, and Reporting Adverse Events and Serious Adverse Events

Throughout the duration of the study, the Investigator will closely monitor each subject for evidence of drug intolerance and for the development of clinical or laboratory evidence of adverse events. All adverse events (expected or unexpected) which occur during the course of the study, whether observed by the Investigator or by the subject, and whether or not thought to be drug-related, will be reported and followed until resolution or until they become stable.

The description of the adverse event will include description of event, start date, stop date, intensity, if it was serious, relationship to test drug, change in test drug dosage, if the subject died, and if treatment was required.

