Events will be recorded as one of the following severity and causality categories below:

Severity	Definition
Mild (Grade 1)	Awareness of signs or symptoms, but no disruption of usual activity
Moderate (Grade 2)	Discomfort sufficient to interfere, but not prevent, daily activity
Severe (Grade 3)	Unable to carry out usual activity
Very severe (Grade 4)	Incapacitating, requires hospitalization, results in death

Category	Definition
Unrelated	Clearly and incontrovertibly due only to extraneous causes, and does not meet criteria listed under possible or probable.
Unlikely	Does not follow a reasonable temporal sequence from administration. May have been produced by the subject's clinical state or by environmental factors or other therapies administered.
Possible	Follows a reasonable temporal sequence from administration, but may have been also produced by the subject's clinical state, environmental factors or other therapies administered.
Probable	Clear-cut temporal association with administration with improvement on cessation of investigational medicinal product or reduction in dose. Reappears upon rechallenge. Follows a known pattern of response to the investigational medicinal product.
Definitely	There is evidence of exposure to the test product, for example, reliable history or acceptable compliance assessment; the temporal sequence of the AE onset relative to the drug is reasonable; the AE is most likely to be explained by the drug treatment than by another cause; the challenge is positive; re-challenge (if feasible) is positive; the AE shows a pattern consistent with previous knowledge of the drug treatment.

Adverse events with the causality assessed as possible or probable are categorized as related to study medication and are called adverse drug reactions.

All SAEs must be reported immediately (no more than 24 hours after becoming aware of the event) by entering the information about the event in the eCRF forms. The Sponsor's Medical Director and Safety Monitor will be notified of the event by the eCRF system. In the case that the eCRF system is not available, the Investigator must contact Medical Director ([name]) or Safety Monitor ([name]) to notify the Sponsor of the event.

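### SAP 11.2 pools very severe with severe adverse events, so the two main TEAE severity tables do not show very severe or related very severe incidence by arm

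*SAP*

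**What the plan says.** Protocol 8.3.2.2 has each adverse event recorded at one of four severity levels: mild (Grade 1), moderate (Grade 2), severe (Grade 3) and very severe (Grade 4). The last is defined as "Incapacitating, requires hospitalization, results in death".

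Protocol 6.2.4 makes the top two grades count differently for permanent discontinuation: "The subject experiences two or more Grade 3 toxicities or one or more Grade 4 toxicity considered by the investigator associated" with either study treatment.

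Protocol 10.4.1 plans "incidence of adverse events by severity within body system" and does not say which levels are to be shown.

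SAP 11.2 then sets the display. A patient with an event classified as very severe "per CTCAE severity in eCRF will be presented in the category" Severe. Two further rules in the same section feed that row:

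- For repeated events of the same preferred term, "the most extreme value (highest severity and closest relationship to study drug) will be used for those patients" concerned.
- "If the severity is missing, the severity of the TEAE will be regarded as severe".

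The table list in SAP 14.1 has one TEAE severity table by system organ class and preferred term (14.3.3.4). It lists no table for the top grade.

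**The concern.** The row labelled Severe carries the name that the protocol gives to Grade 3 alone, but it holds Grade 3, Grade 4 and ungraded events. A reader comparing the arms cannot tell from the two main severity tables whether a given number of severe events consists of Grade 3 events or includes some at the worst level recorded.

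The protocol treats that distinction as meaningful for the individual patient: one related Grade 4 toxicity is enough for permanent discontinuation, while Grade 3 requires two. Safety is also half of the stated objective (protocol section 5, SAP 2.1). At stake is how informative the descriptive safety comparison is. No efficacy result is affected.

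**Working it through.** The plan states no figure to reproduce, and the documents give no Grade 4 rate. The check is a comparison of sections and a count of rows.

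**1. Rows in the TEAE overview (SAP 11.2, Table 14.3.3.1).** The section lists 13 parameters: any; related; mild or moderate; related mild or moderate; severe; related severe; serious; non-serious; related serious; leading to withdrawal; related leading to withdrawal; leading to death; related leading to death. Four concern severity. None isolates very severe.

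**2. What the Severe row contains.** In each arm, counting events:

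Severe (displayed) = Grade 3 + Grade 4 + missing severity

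Related severe is the related subset of the same sum. There is one displayed total and three components, so the Grade 4 component cannot be recovered from the row. The same holds for patient counts, except that a patient with events in more than one component is counted once.

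**3. Whether the worst-value rule helps.** It does not. It selects the highest severity per preferred term, but after pooling, a patient whose worst event is Grade 4 falls in the same row as one whose worst is Grade 3. Table 14.3.3.4 can therefore show at most three of the four recorded levels.

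**4. Whether other rows isolate the top level.**

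| Row | Relation to very severe |
|---|---|
| Serious, related serious | Large overlap, because the Grade 4 wording includes hospitalization and death, and both are seriousness criteria in protocol 8.3.2.1. Not the same set: that list also has "Is an important medical event", and protocol section 4 reports from earlier PRX-102 studies that "One patient experienced a Grade 3 hypersensitivity related serious adverse event of bronchospasm". |
| Leading to death | Fatal events only. |
| Leading to withdrawal | Mixes the Grade 3, Grade 4 and hypersensitivity routes of protocol 6.2.4. |

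These rows cover much of the ground, but none gives the very severe count.

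**5. Which scale the grade follows.** Protocol 6.2.4 and SAP 11.2 refer to CTCAE. Protocol 8.3.2.2 gives its own definitions. The documents do not settle which one the eCRF field holds.

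**6. Infusion-related reactions.** SAP 11.2.1 lists six overview parameters, two on severity (mild or moderate; severe), and has no very severe row. It does not repeat the pooling rule. That the rule applies there is an inference, and the shells (SAP section 15) are a separate document.

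**The case against.** The strongest case against is that this is a disclosed presentation choice.

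- **No protocol rule is broken.** Protocol 10.4.1 names no levels, and very severe incidence is not a listed safety endpoint (SAP 2.2.4). The SAP states the pooling openly, and Grade 4 events go into the worst displayed row. This stands.
- **The discontinuation rule is for managing patients and does not define an analysis category.** Its enforcement is handled elsewhere: SAP 4.4 treats patients who met a discontinuation criterion but continued as potential major violations for the per-protocol set, under blinded review, and SAP 8.1 tabulates major and critical deviations by type. This stands. What remains is that the protocol itself treats the two grades differently, which is a reason to show them apart.
- **Other outputs already show most such events by arm.** These are the serious, related serious and death rows, the serious-event tables 14.3.3.6 and 14.3.3.7, and the event listings with severity. With 78 patients, a hand count is feasible. This largely stands, subject to one gap: the SAP does not say whether the listings show the recorded grade or the pooled one.
- **The scale is unsettled.** A very severe row might therefore not count exactly the Grade 4 toxicities of protocol 6.2.4. This is fair, and it is why the fix includes a footnote.

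A reader might also infer three stronger things that the documents do not support. The first is that the SAP contradicts the protocol; it does not, as above. The second is that every table with a severity row is affected, including all those for infusion reactions; the pooling is stated only in 11.2. The third is that the gap touches trial success, because protocol 6.2 speaks favourably of a better safety profile. Formal success is defined on non-inferiority of the eGFR slope (SAP 7.6.1).

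**Conclusion.** The point holds as a small reporting improvement. As written, Tables 14.3.3.1 and 14.3.3.4 do not show very severe events by arm, and the overview does not show related very severe events either. The pooled row also carries a label that the protocol reserves for Grade 3.

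The size is two tables: 0 of 13 overview rows isolate the level, and one of four recorded levels is lost to this pooling. The number of events hidden is unknown and may be zero. The conclusion assumes that the unseen shells follow the text of 11.2. That most very severe events also surface as serious, fatal or leading to withdrawal assumes that the eCRF grade follows the wording of protocol 8.3.2.2. It is a loss of descriptive detail. It is not an error against the protocol, and no inference on efficacy depends on it.

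**What to change.** 1. Label the pooled row 'Severe or very severe' in both tables. Keep the rule for missing severity, counted in that row only.
2. Add 'Very severe' and 'Related very severe' rows to Table 14.3.3.1 (13 + 2 = 15 rows).
3. Add a 'Very severe' level to Table 14.3.3.4.
4. State in a footnote which scale the eCRF grade uses: CTCAE or the definitions in protocol 8.3.2.2.
5. Check the shells for the infusion-reaction overview and severity tables. If the pooling applies there, make the same change. No related row is needed, because SAP 11.2.1 defines these reactions as related.

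The cost is a few programming lines and one footnote. The eCRF already holds the grade, and SAP section 15 says the shells were to be updated for the final analysis anyway. The downside is that some rows will be sparse or zero. With 52 and 26 patients randomized as planned, one patient is 1/52 = 1.9% in the PRX-102 arm and 1/26 = 3.8% in the agalsidase beta arm, so the added rows should be read as counts and support no formal comparison.
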